5.6. Safety Monitoring and Study Drug Interruption/Dose Modification/Discontinuation

Required and recommended actions for discontinuation or dose modification for both drugs, including the combination regimen, are provided in [Table 5-3](#). The requirements and recommendations are based on the drug and the CTCAE grade of specific toxicities, focusing on the types of events most commonly attributed to each of the study agents.

In cases of uncertainty, the study medical monitor should be contacted.

There is no limit on the length of time either idelalisib or BI 836826 may be held during the study (eg, to allow resolution of toxicity). If both idelalisib and BI 836826 are held during the same period, when appropriate both drugs should be restarted on the same day rather than dosing with idelalisib for 7 days prior to restarting BI 836826. During the combination therapy period (through Week 46), if either study drug is permanently discontinued, the other study drug should also be permanently discontinued. See Section [6.6.1](#) for recommended follow-up.

Table 5-3. Requirements and Recommendations for Discontinuation or Modification of Study Treatment in Response to Adverse Events

NCI CTCAE Grade ¹	Idelalisib	BI 836826
HEMATOLOGICAL ADVERSE EVENT		
Neutropenia		
Grade ≤ 2 neutropenia	Maintain current dose and schedule.	Maintain current dose level and schedule.
Grade 3 neutropenia	Required action: Blood counts must be monitored at least weekly until neutropenia Grade ≤ 2 .	Maintain current dose level and schedule. Consider G-CSF support. If febrile neutropenia not resolving within 48 hrs with appropriate treatment, decrease subsequent dose by 50% ² .
Grade 4 neutropenia (or occurrence of neutropenic fever or infection)	Required action: Interrupt idelalisib. Blood counts must be monitored at least weekly until neutropenia is \leq Grade 2. Recommended action: May resume idelalisib at lower dose level when neutropenia is Grade ≤ 3 ² . Neutropenia should be managed according to established clinical guidelines.	If Gr 4 neutropenia lasts >7 days, or febrile neutropenia not resolving within 48 hrs with appropriate treatment, decrease subsequent dose by 50% ³ Otherwise, maintain current dose level and schedule and consider G-CSF support.
Thrombocytopenia		
Grade ≤ 2 thrombocytopenia	Maintain current dose and schedule.	Maintain current dose level and schedule.

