Grade 3 thrombocytopenia	Maintain current dose and schedule.	Maintain current dose level and schedule; unless associated with significant bleeding, in which case decrease subsequent dose by 50% ³
Grade 4 thrombocytopenia	Required action: During continuing single agent therapy period, withhold for bruising or bleeding until Grade ≤ 3 . Recommended action: During combination therapy period, maintain current dose level. If withheld during continuing therapy period, may resume at same or reduced dose level at investigator discretion ² .	If lasts > 7 days or associated with significant bleeding, decrease subsequent dose by 50% ³ .
Anemia		
Grade ≤ 3	Maintain current dose and schedule.	Maintain current dose level and schedule.
Grade 4	If all other possible etiologies of anemia have been ruled out, idelalisib may be withheld at investigator discretion.	Decrease subsequent dose by 50% ³ .

NCI CTCAE Grade ¹	Idelalisib	BI 836826
NON-HEMATOLOGICAL ADVERSE EVENT		
Rash		
Grade ≤ 2	Maintain current dose and schedule.	Maintain current dose level and schedule.
Grade ≥ 3	Required action: Withhold idelalisib until Grade ≤ 1. Recommended action: May resume at lower dose or discontinue idelalisib at investigator discretion ² .	Delay BI 836826 until Grade ≤ 1. Thereafter, may resume at full dose.
Stevens-Johnson Syndrome/Toxic Epidermal Necrolysis		
Any Grade	Required action: Discontinue idelalisib. Interrupt coadministered medications potentially associated with SJS or TEN. Institute treatment per institutional standards.	Discontinue BI 836826. Institute treatment per institutional standards.
Bowel Perforation		
Any Grade	Discontinue idelalisib.	Discontinue BI 836826.
Diarrhea or Colitis		
Any Grade (in addition see below for response to specific CTCAE grades)	Required action: See Section 5.7.2.1 for required assessments. Recommended action: Ensure good hydration status and provide anti-diarrheal; maintain current dose level. See Section 5.7.2.2 for recommended evaluations.	See below.
Grade ≤ 1	Required action: See Section 5.7.2.1 for required assessments. Recommended action: Provide anti-diarrheal (eg, loperamide) and maintain current idelalisib dose and schedule.	Maintain current dose level and schedule.

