Grade 4 (ALT/AST > 20 × ULN; Bilirubin > 10xULN)	Required action: Withhold idelalisib. Monitor ALT, AST, ALP, and bilirubin at least 1x per week until all abnormalities are Grade ≤1. If bilirubin abnormality was Grade 4, discontinue idelalisib. Recommended action: If bilirubin abnormality was Grade <4 resume idelalisib at lower dose level ² .	Withhold BI 836826. Monitor ALT, AST, ALP, and bilirubin at least 1x per week until all abnormalities are Grade ≤1. If bilirubin abnormality was Grade 4, discontinue BI 836826.
Pneumonitis (with new onset or worsening of baseline dyspnea, cough, or hypoxia without obvious infectious cause)		
Grade 1 (asymptomatic)	Required action: Withhold idelalisib until resolution to baseline. May resume at lower dose level or discontinue at investigator discretion.	Maintain current dose level and schedule.
Grade ≥ 2	Required action: Discontinue idelalisib permanently in subjects with any severity of symptomatic pneumonitis and institute therapy as clinically appropriate.	Discontinue BI 836826.
Pneumocystis jirovecii pneumonia (PJP)		
Any Grade	Required action: Discontinue idelalisib.	Discontinue BI 836826.
CMV Infection/Reactivation⁴		
Any Grade	Required action: Interrupt idelalisib upon unequivocal clinical or laboratory evidence of CMV infection. Treat according to established clinical guidelines. If the benefits of resuming idelalisib are judged to outweigh the risks, consider pre-emptive CMV therapy.	Discontinue BI 836826.
Hepatitis B Reactivation		
Any Grade	Required action: Discontinue idelalisib.	Discontinue BI 836826.

NCI CTCAE Grade ¹	Idelalisib	BI 836826
OTHER NONHEMATOLOGICAL ADVERSE EVENTS		
Grade ≤ 2	Maintain current dose level and schedule.	Maintain current dose level and schedule.
Grade ≥ 3	Withhold study drug until Grade ≤ 1. May resume study drug at initial or next lower dose ² or discontinue study drug at investigator discretion.	Withhold study drug until Grade ≤ 1. May resume study drug at initial or at 50% ³ or discontinue study drug at investigator discretion.

1. CTCAE, Version 4.03.
2. If assigned idelalisib dose level is 50 mg BID, dose reduction is not possible and idelalisib should be interrupted.
3. Dose reduction of BI 836826 by 50% may be performed twice. If still not tolerated, BI 836826 should be discontinued.
4. CMV should be diagnosed using clinical or laboratory criteria per established institutional standard

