5.7.6. Infectious Events

Patients with lymphoid cancers receiving idelalisib have developed serious and fatal infections during therapy. Opportunistic infections, most notably *Pneumocystis jirovecii* pneumonia (PJP) and CMV infection, have most frequently occurred within the first 6 months of treatment with idelalisib and are increased in the context of concurrent myelosuppressive therapy such as bendamustine.

Subjects must receive prophylaxis for PJP throughout the course of idelalisib treatment, and for 2 to 6 months after idelalisib treatment ends (see Section 5.8.1). Subjects must permanently discontinue idelalisib upon diagnosis of PJP.

Cytomegalovirus (CMV) surveillance for active disease (quantitative PCR or PP65 antigen) must be conducted approximately every 4 weeks throughout the course of idelalisib treatment. CMV viral load testing should be performed from the same specimen type whenever possible and caution should be exercised when comparing CMV viral load results across different testing centers. If unequivocal clinical or laboratory evidence of CMV infection is present, the subject must interrupt idelalisib treatment and undergo effective antiviral treatment according to established clinical guidelines. If the benefits of resuming idelalisib are judged to outweigh the risks, consider pre-emptive CMV therapy.

In high-risk subjects (history of recurrent infection, allogeneic transplant, treatment with alemtuzumab, hypogammaglobulinemia) other infection prophylaxis should be considered per consensus guidelines. Administration of intravenous immunoglobulin is permitted per standard institutional practice {[Raananani 2009](#)}. For subjects who develop an infection, appropriate medical therapy should be instituted in a timely manner.

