6.6. Criteria for Discontinuation from Treatment or Study

6.6.1. Criteria for Discontinuation of Study Drug

Study drug may be discontinued in the following instances, in consultation with the Gilead Medical Monitor:

- Disease progression

- Initiation of non-study specific anti-cancer therapy in the absence of progression
- If, in the investigator's opinion, it is not in the subject's best interest to continue.
- Pregnancy or breastfeeding begins during the study
- Subject non-compliance
- Subject request to discontinue study drug, for any reason
- Any subject is unable to tolerate a second rechallenge for the same AE
- Toxicity for which the protocol specifies discontinuation of study drug
- Any subject whose benefit-risk profile is not deemed positive by the investigator must discontinue study drug
- During the combination therapy period (through Week 46), if either study drug is permanently discontinued, the other study drug should also be permanently discontinued

End of Treatment (EOT) assessments as specified in [Appendix 2](#) will be performed when a subject permanently discontinues both BI 836826 and idelalisib.

Subjects who permanently discontinue study drug for a reason other than disease progression should continue with disease assessments per the schedule of procedures until disease progression, study participation has ended, or another anticancer or experimental therapy is initiated (see [Appendix 2](#)).

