6.6.2. Criteria for Discontinuation from Study

Discontinuation from the study may occur in the following instances:

- Disease progression
- Initiation of non-study specific systemic anti-cancer therapy in the absence of progression
- If, in the investigator's opinion, and in consultation with Gilead Sciences, it is determined not to be in the subject's best interest to continue.
- Pregnancy begins during the study
- Death
- Discontinuation of the study at the request of Gilead, a regulatory agency, or an institutional review board or independent ethics committee (IRB/IEC) occurs

- Withdrawal of consent
- Subject is lost to follow-up

If a subject discontinues the study for reasons other than withdrawal of full consent, lost to follow-up, or death, the subject will complete a 30-Day Follow-up/End of Study visit (see Section 6.7). Note that pregnancies are monitored until the conclusion of the pregnancy even after discontinuation from the study (see Section 7.7.2.1).

6.7. 30-Day Follow-up/End of Study Visit

A 30-Day Follow-up/End of Study assessment will be performed 30 days following the last dose of BI 836826 (no later than Week 50) however, it may be waived for subjects who have permanently discontinued study drug and have had a study visit > 30 days after the last dose.

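### The Table 5-3 CMV row stops BI 836826 but leaves idelalisib open to restart, with no period limit, while Sections 5.6 and 6.6.1 take the subject off both drugs through Week 46

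*Protocol*

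**What the plan says.** Section 6.6.1 of the protocol lists this among the criteria for stopping treatment: "During the combination therapy period (through Week 46), if either study drug is permanently discontinued, the other study drug should also be permanently discontinued". Section 5.6, in the text that introduces Table 5-3, states the same rule for the same period: "if either study drug is permanently discontinued, the other study drug should also be permanently discontinued". Neither place names an exception. Section 5.6 also says: "In cases of uncertainty, the study medical monitor should be contacted".

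The CMV row of Table 5-3 applies to any grade. Its idelalisib column begins "Interrupt idelalisib upon unequivocal clinical or laboratory evidence of CMV infection", then asks for treatment and addresses antiviral cover should idelalisib be resumed. Its BI 836826 column says to discontinue. The row names no treatment period.

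Section 5.7.6 repeats the idelalisib part, including "If the benefits of resuming idelalisib are judged to outweigh the risks, consider pre-emptive CMV therapy". It gives no BI 836826 action for CMV and does not refer to the joint-stop rule.

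**The concern.** For a CMV infection before Week 46, two parts of the protocol point to different actions on idelalisib. Sections 5.6 and 6.6.1 take the subject off both drugs for good once BI 836826 is permanently discontinued. The CMV row and Section 5.7.6 treat the idelalisib stop as temporary and speak of resuming it on a benefit-risk judgment.

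What is at stake is a stop-or-restart decision after an infection that the protocol itself treats as serious. Section 5.7.6 reports serious and fatal infections with idelalisib, names CMV among the most notable opportunistic ones, and places most of those in the first 6 months of treatment, inside the combination period. CMV testing about every 4 weeks was kept after the early termination (Section 6.1.8.7 and Appendix 2), and laboratory evidence alone can trigger the row. Whether a subject goes back on idelalisib should not depend on which section the site opens first.

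**Working it through.** No sample size, power or event figure is involved, so the check is a comparison of texts.

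**1. Does *discontinue* in the CMV row mean permanently?** The row omits the word *permanently*. For temporary BI 836826 stops, however, Table 5-3 uses *delay* or *withhold*. It uses plain *discontinue* for SJS/TEN, bowel perforation, PJP and hepatitis B reactivation. Within the CMV row, *interrupt* for one drug stands against *discontinue* for the other. Permanent is the natural reading, so the joint-stop rule is triggered.

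**2. How does the row compare with the others that direct BI 836826 to be discontinued?**

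| Table 5-3 row | BI 836826 | Idelalisib |
|---|---|---|
| SJS/TEN, any grade | discontinue | discontinue |
| Bowel perforation, any grade | discontinue | discontinue |
| Grade 4 hepatic with Grade 4 bilirubin | discontinue | discontinue |
| Pneumonitis, Grade ≥ 2 | discontinue | discontinue permanently |
| PJP, any grade | discontinue | discontinue |
| Hepatitis B reactivation, any grade | discontinue | discontinue |
| CMV, any grade | discontinue | interrupt; resumption contemplated |

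That makes 7 rows, of which 6 stop both drugs and 1 does not. The pneumonitis row shows how plainly the table can say it: "Discontinue idelalisib permanently in subjects with any severity of symptomatic pneumonitis and institute therapy as clinically appropriate". Not counted are the row for other non-hematological events of Grade ≥ 3, where stopping either drug is at the investigator's discretion, and footnote 3, which concerns failed dose reductions.

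**3. Could the resumption wording be meant only for the single-agent period?** The row does not say so. The table does separate the periods where it wants to, as in the Grade 4 thrombocytopenia row: "During continuing single agent therapy period, withhold for bruising or bleeding until Grade" (the grade limit follows).

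**4. When does the row's BI 836826 instruction operate?** Only while infusions are still due.
- Infusions are scheduled from Week 2 through Week 46 (Section 5.4.2): 46 − 2 + 1 = 45 weeks, all within the joint-stop rule.
- The latest permitted infusion is in Week 48: 48 − 46 = 2 further weeks outside the rule.
- Under Section 6.5, single-agent idelalisib after the final infusion lasts 4 weeks, to Week 50.

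The row's two columns therefore apply together almost only in the period when the joint-stop rule would override the idelalisib column.

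**5. Result for a CMV event before Week 46.** Under the row or Section 5.7.6, idelalisib is interrupted and possibly resumed; the row also stops BI 836826. Under Sections 5.6 and 6.6.1, both drugs should be stopped permanently.

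**The case against.** The strongest reply is that the texts can be applied together. Table 5-3 gives actions drug by drug, Section 5.6 adds the joint-stop rule on top, and the combined answer through Week 46 is to stop both. That stands: no site is forced to break one rule to keep another, and reading this as an outright contradiction goes too far. The cost of that reading is that the row's idelalisib column is left with almost nothing to do in the period the row addresses.

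It can also be said that the resumption sentence is conditional and gives advice on antiviral cover, not permission to restart. That is fair as grammar, but the sentence presupposes that restarting is open, and nothing beside it says otherwise. It keeps a proper use for single-agent idelalisib after the last infusion, which is where the fix would place it.

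A reader might infer that CMV is the only place where the table fails to carry through the joint-stop rule. It is not. The Grade 1 pneumonitis row and the Grade ≥ 3 rash and diarrhea rows let idelalisib be discontinued at discretion without a matching BI 836826 stop. The Grade 4 infusion-reaction instruction (Table 5-2) and footnote 3 of Table 5-3 end BI 836826 and say nothing of idelalisib. All of these leave the other drug's action to Section 5.6. CMV differs in one respect: it stops BI 836826 and expressly contemplates restarting idelalisib.

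A reader might also look to Section 6.7, where "A 30-Day Follow-up/End of Study assessment will be performed 30 days following the last dose of BI 836826", and infer that resuming after CMV would bring a subject to the final visit still on idelalisib. The documents do not support that as a consequence of the CMV row. Section 6.5 already keeps every subject on idelalisib after the final infusion until the Week 50 assessments, and Section 7.3.2 collects adverse events until 30 days after whichever drug stops last.

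The medical monitor is already the contact for uncertainty under Section 5.6, and Section 6.6.1 calls for consultation on stopping drug. Both limit the harm. They help less where a site reads only the CMV row or Section 5.7.6 and sees nothing uncertain.

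**Conclusion.** The point holds as an unclear safety instruction. Sections 5.6 and 6.6.1 state a joint stop through Week 46 without exception; the CMV row and Section 5.7.6 leave room to restart idelalisib without a period limit.

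The reach is small. At most the 2 enrolled subjects are affected. Section 5.4 says that they may remain on study at their current doses of both drugs; it does not establish that both are still receiving both, and a reader should not assume so. The joint-stop rule is worded *should*. The SAP lists safety data by subject (Sections 3, 7.1.6 and 7.7), so no estimate changes. The documents give no CMV incidence, so the chance of the event is not estimated.

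The conclusion assumes that *discontinue* in the CMV row means permanently, as the table's own usage indicates. It does not assume which outcome the sponsor intended. It merits correction because it governs re-exposure after a serious infection and costs little to put right.

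**What to change.** In the Table 5-3 CMV row and in Section 5.7.6, limit resumption of idelalisib to single-agent treatment after the combination period, and state that CMV infection through Week 46 discontinues both drugs as Sections 5.6 and 6.6.1 require. If the sponsor does intend resumption during the combination period, leave the row and write an explicit CMV exception into Sections 5.6 and 6.6.1.

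Either route changes wording in two places and needs no new data collection. It is a protocol modification, so Section 9.2.1 requires IRB/IEC approval first. Until then, remind the sites to take any CMV event through Week 46 to the medical monitor before restarting idelalisib. Section 5.6 already supports this, so the reminder alters no rule.

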6.6.2. Criteria for Discontinuation from Study

Discontinuation from the study may occur in the following instances:

- Disease progression
- Initiation of non-study specific systemic anti-cancer therapy in the absence of progression
- If, in the investigator's opinion, and in consultation with Gilead Sciences, it is determined not to be in the subject's best interest to continue.
- Pregnancy begins during the study
- Death
- Discontinuation of the study at the request of Gilead, a regulatory agency, or an institutional review board or independent ethics committee (IRB/IEC) occurs

- Withdrawal of consent
- Subject is lost to follow-up

If a subject discontinues the study for reasons other than withdrawal of full consent, lost to follow-up, or death, the subject will complete a 30-Day Follow-up/End of Study visit (see Section 6.7). Note that pregnancies are monitored until the conclusion of the pregnancy even after discontinuation from the study (see Section 7.7.2.1).

6.7. 30-Day Follow-up/End of Study Visit

A 30-Day Follow-up/End of Study assessment will be performed 30 days following the last dose of BI 836826 (no later than Week 50) however, it may be waived for subjects who have permanently discontinued study drug and have had a study visit > 30 days after the last dose.

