6.5. Treatment and Post-Treatment Period Assessments

Study days will be determined based on the first administration of idelalisib on Week 1, Day 1. All subjects will receive 7 days of idelalisib monotherapy followed by a period of combination therapy with idelalisib plus intermittent BI 836826 infusions. After the final BI 836826 infusion subjects will continue to receive idelalisib monotherapy for 4 weeks, through completion of Week 50 assessments.

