7.3.2. Adverse Events

Following initiation of study medication, collect all AEs, regardless of cause or relationship, until 30 days after last administration of idelalisib or BI 836826 (whichever is discontinued last), and report in the eCRF database as instructed.

All AEs should be followed up until resolution or until the adverse event is stable, if possible. Gilead Sciences may request that certain AEs be followed beyond the protocol defined follow up period.

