7.3.3. Serious Adverse Events

All SAEs, regardless of cause or relationship, which occur after the subject first consents to participate in the study (ie, signing the informed consent) and throughout the duration of the study, including the protocol-required post treatment follow-up period, must be reported to the eCRF database and Gilead Drug Safety and Public Health (DSPH) as instructed. This also includes any SAEs resulting from protocol-associated procedures performed after informed consent is signed.

Any SAEs and deaths which occur after the post treatment follow-up visit but within 30 days of the last dose of study drug (idelalisib or BI 836826, whichever is later), regardless of causality, should also be reported.

Investigators are not obligated to actively seek SAEs after the protocol defined 30-day follow up period. However, if the investigator learns of any SAEs that occur after study participation has concluded and the event is deemed relevant to the use of IP, he/she should promptly document and report the event to Gilead DSPH.

All AEs and SAEs will be recorded in the eCRF database within the timelines outlined in the eCRF completion guideline.

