BI 836826 Administration ⁷		X		X	X	X	X	X	X	
Adverse Events		X		X	X	X	X	X	X	X
Concomitant Medication		X		X	X	X	X	X	X	X

1 Chemistry & hematology will be obtained a minimum of 3 times in the first week following completion of the first 50% dose of BI 836826 on Day 9; and once after the first full dose of BI 836826 on Day 22, then a minimum of weekly x 6 weeks, then prior to each BI 836826 infusion. All subjects should have blood counts monitored at least every two weeks for the first 6 months of idelalisib treatment. For subjects who develop ANC 0.5 to < 1.0 Gi/L, blood counts should be monitored at least weekly

2 CMV surveillance for active disease must be conducted approximately every 4 weeks throughout the course of idelalisib treatment.

3 Samples for immune monitoring were drawn at Baseline prior to the first dose of idelalisib. With the implementation of Amendment 4, only CD4 will be collected at the time points specified.

- 4 With the implementation of Amendment 4, PK and biomarker samples are no longer being collected and subjects are past Week 16. Samples for BI 836826 anti-drug antibody testing will be drawn at the time points indicated. For additional information see [Appendix Table 2](#) PK and Anti-Drug Antibody Sampling and the Laboratory Manual.

■

- 6 Idelalisib is taken BID; on BI 836826 dose days the morning dose is taken in the clinic approximately 60 minutes prior to starting the BI 836826 infusion
- 7 BI 836826 given via IV infusion at the indicated time points, beginning with 10 mg and ramping up through 50% to 100% of the intended dose over 4 weeks
- 8 The 30-day Follow-up assessment will be done following last dose of BI 836826 (no later than Week 50).

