Appendix Table 2. PK and Anti-Drug Antibody Sampling

With the implementation of Amendment 4, PK samples are no longer being collected and subjects are past Week 16.

Study Day	Study Week	BI 836826 PK	ADA analysis	Idelalisib PK
8	2	Before start of BI 836826 drug infusion	Before start of BI 836826 drug infusion	Within 30 min prior to idelalisib dose
		Shortly before end of infusion		1.5 hr after idelalisib dose
9	2	Before start of BI 836826 drug infusion		
		Shortly before end of infusion		
15	3	Before start of BI 836826 drug infusion		
		Shortly before end of infusion		
22	4	Before start of BI 836826 drug infusion		Within 30 min prior to idelalisib dose
		Shortly before end of infusion		1.5 hr after idelalisib dose
23	4	8-10 hr after start of drug infusion		
[25-27]		23-25 hr after start of drug infusion		
36 to 106	6 through 16	72-120 hr after start of drug infusion		
		Before start of BI 836826 drug infusion	Weeks 6, 10, and 14 Before start of BI 836826 drug infusion	Weeks 6 and 14: within 30 min prior to, and 1.5 hr after idelalisib dose
	18	Shortly before end of infusion (Weeks 6, 10, and 14 only)		
			Before start of BI 836826 drug infusion	
120				
176 to 316	26 through 46		Weeks 26, 34, and 42 Before start of BI 836826 drug infusion	
344	30d follow up/EOS		At any time during the visit	

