#### 7.1.5. Treatment-Emergent Adverse Events

##### 7.1.5.1. Definition of Treatment-Emergent Adverse Events

Treatment-emergent adverse events (TEAEs) are defined as 1 or both of the following:

- Any AEs with an onset date on or after the study drug start date and no later than 30 days after permanent discontinuation of study drug
- Any AEs leading to premature discontinuation of study drug.

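### For a subject who completes treatment, the 30-Day Follow-up falls on about the last idelalisib day, so no contact is scheduled in the 30-day safety window that follows

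*Protocol*

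**What the plan says.** **Closing visit.** Protocol section 6.7 says that the 30-Day Follow-up/End of Study assessment "will be performed 30 days following the last dose of BI 836826 (no later than Week 50"). Footnote 8 to the study procedures table in Appendix 2 repeats the rule: "The 30-day Follow-up assessment will be done following last dose of BI 836826 (no later than Week 50"). SAP Appendix 1 carries the same footnote. Protocol Appendix Table 2 puts the row "30d follow up/EOS" on Study Day 344. Section 6.1 allows ±7 days. Section 6.7 also waives the visit for a subject off study drug who has been seen more than 30 days after the last dose, without saying of which drug.

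**Idelalisib.** Section 6.5: "After the final BI 836826 infusion subjects will continue to receive idelalisib monotherapy for 4 weeks, through completion of Week 50 assessments".

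**Safety windows.** Section 7.3.2 requires collection of all adverse events "until 30 days after last administration of idelalisib or BI 836826 (whichever is discontinued last"). Section 7.3.3 also requires reporting of serious events and deaths "which occur after the post treatment follow-up visit but within 30 days of the last dose of study drug", counted from the later drug. SAP 7.1.5.1 counts an event as treatment-emergent if its onset is "no later than 30 days after permanent discontinuation of study drug". SAP 7.2.1.1 uses the same 30 days for laboratory abnormalities.

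**End of Treatment.** Section 6.6.1 refers to Appendix 2 for End of Treatment assessments, which "will be performed when a subject permanently discontinues both BI 836826 and idelalisib". The current Appendix 2 has no such column.

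**The concern.** The visit is called a 30-day follow-up, but for a completer it follows only one of the two drugs. The protocol's own safety window is set by the drug stopped last, which for a completer is idelalisib. The schedule therefore ends at about the point where that window opens.

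Sections 2 and 8 say that, after early termination, the enrolled subjects are assessed for safety only. What is at stake is how completely the study finds adverse events in the month after idelalisib. With no named contact, that depends on the subject volunteering information or on the site calling on its own initiative.

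**Working it through.** **Inputs**

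- Last planned infusion: Week 46, Day 316 (Appendix 2 study procedures table).
- Idelalisib after the last infusion: 4 weeks (6.5).
- Closing visit: Day 344 (Appendix Table 2), ±7 days (6.1).
- Safety window: 30 days after the later drug (7.3.2; SAP 7.1.5.1 and 7.2.1.1).

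**1. Reproduce the plan's days.** The first day of week *w* is 7(*w* − 1) + 1. For Week 46: 7 × 45 + 1 = 316. For Week 50: 7 × 49 + 1 = 344. Both match the protocol tables. Week 50 covers Days 344 to 350.

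**2. Completer, tabulated visit day.** Last idelalisib = 316 + 28 = Day 344. Visit minus last idelalisib = 344 − 344 = 0 days. The safety window ends on 344 + 30 = Day 374.

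**3. Completer, strict 30 days after BI 836826.** 316 + 30 = Day 346, still in Week 50. That is 346 − 344 = 2 days after a four-week idelalisib course, or 0 days if idelalisib continues until those assessments, as 6.5 also allows.

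**4. Completer, full visit window.** 344 + 7 = Day 351, which is 7 days after idelalisib and leaves 374 − 351 = 23 days. This is generous, because Week 50 ends on Day 350.

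**5. Early stop.** Before Week 46 both drugs stop together (6.6.1). If they stop *k* days after the last infusion, the visit falls 30 − *k* days after idelalisib. With four-weekly infusions on schedule, *k* runs from 0 to 28, so the visit falls 30 to 2 days after idelalisib.

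| Case | Closing visit | Days after last idelalisib | Days of the 30 left after the visit |
|---|---|---|---|
| Completer, tabulated day | Day 344 | 0 | 30 |
| Completer, strict 30 days | Day 346 | 2 | 28 |
| Completer, full +7 days | Day 351 | 7 | 23 |
| Early stop on an infusion day | infusion + 30 | 30 | 0 |
| Early stop 28 days after an infusion | infusion + 30 | 2 | 28 |

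**6. Is anything scheduled later?** No column follows the End of Study visit in either schedule. Unscheduled visits (6.8) apply while a subject is on study, and participation ends at about Week 50 (section 6). Hepatitis B monitoring (5.7.11) applies only to subjects positive for core antibody at screening, and on-protocol testing is limited to study participation.

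**The case against.** The best defence is that this is a deliberate close-out. The phrase about staying on study to about Week 50, including follow-up after the last BI 836826 dose, recurs throughout the protocol. BI 836826 is the investigational agent, and idelalisib is already approved for relapsed CLL (1.2.1). Section 7.3.2 already obliges sites to collect events to 30 days after the later drug and to follow them to resolution or stability where possible. Section 7.3.3 expressly foresees events after the visit. At most two subjects are involved, and the SAP only lists their data, so no rate, estimate or dose decision changes.

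Most of this stands, and it limits the size of the point. It does not supply the missing contact. Section 7.3.3 also releases investigators from actively seeking serious events once the 30-day follow-up period is over. With the visit tied to BI 836826, a site could take that period to end at Week 50.

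A reader might infer more than the documents support:

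- *That events in the last month are not collected.* They are reportable. Only scheduled ascertainment is missing.
- *That laboratory draws were promised.* The SAP windows classify whatever data exist. Routine CMV surveillance is tied to the course of idelalisib (5.7.6), and two-weekly blood counts to its first 6 months (5.7.5).
- *That the protocol shows new toxicity in this month.* The 7.1-month median in 5.7.2 is time to onset of Grade 3 or 4 diarrhea or colitis among idelalisib-treated patients, not onset after stopping. The time to resolution concerns events already present at interruption.
- *That prophylaxis for Pneumocystis pneumonia and CD4 recovery strengthen the case.* Section 5.8.1 sets a period of 2 to 6 months under clinical judgment, which one contact near Day 374 would not cover.
- *That a skipped infusion puts the visit before the stop date.* This is hypothetical, make-up doses are allowed (5.4.2.3), and neither subject is documented to have had it.
- *That a Week 48 infusion contradicts the cap.* Thirty days after Day 330 is Day 360, so the visit window opens on Day 353. The cap plus 7 days ends on Day 350 + 7 = Day 357. Days 353 to 357 overlap, so the tension is minor.

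**Conclusion.** The point holds as a mismatch between the visit schedule and the protocol's own safety window. For a completer on the planned calendar, the 30-Day Follow-up falls 0 days after idelalisib, or at most 7 with the full window. Between 23 and 30 days of the window then have no scheduled contact. An early stop is not free of the problem: up to 28 days can be left when both drugs stop at the end of a four-week interval, and none when they stop on an infusion day.

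This assumes infusions on schedule, idelalisib stopped on Day 344 for a completer, and, for an early stop, both drugs ended on the same day. The documents do not show whether either subject completes treatment. It is a cheap improvement for at most two people, not a flaw that invalidates the safety listing.

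**What to change.** - **Section 6.7 and footnote 8 (protocol and SAP copy):** time the 30-Day Follow-up from the last dose of idelalisib or BI 836826, whichever is later, as 7.3.2 already does.
- **Waiver in 6.7:** make it refer to that same date.
- **Week 50 cap:** lift it for this contact only, and adjust the statements that participation ends at about Week 50.
- **Content:** an adverse event and serious adverse event check, which may be by telephone. Laboratory tests are optional, if clinically indicated.
- **Week 50:** keep its assessments as End of Treatment for completers. This also gives the End of Treatment reference in 6.6.1 something to point to. The added contact then falls at about Day 374.

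The cost is one contact for each of at most two subjects, the text edits with IRB approval, and about 30 more days before database finalization. Section 7.3.2 already requires adverse event data to that date.
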